8.2 Safety and Other Assessments

Patients will have a set of vital signs obtained prior to initiation of treatment and after 30 minutes of treatment. During this time, patients will be observed in the ED. Either the treating physician who performed the intervention or the CRC will follow up with patients via phone call 24 to 36 hours after the procedure to determine the presence of complications.

8.3 Adverse Events and Serious Adverse Events

8.3.1 ***Definition of Adverse Events (AE)***

An adverse event (AE) is any untoward medical occurrence associated with the use of an intervention in humans, whether or not considered intervention related. Intercurrent illnesses or injuries should be regarded as adverse events.

A pre-existing condition should be recorded as an adverse event if the frequency, intensity or the character of the condition changes.

8.3.2 ***Definition of Serious Adverse Events (SAE)***

Serious Adverse Events (SAE)

Adverse events are classified as serious or non-serious. A serious adverse event is any AE that, in the view of either the investigator or the sponsor, is:

- fatal
- life-threatening

- requires or prolongs hospital stay
- results in persistent or significant disability or incapacity
- a congenital anomaly or birth defect
- an important medical event when the event does not fit the other outcomes, but the event may jeopardize the patient and may require medical or surgical intervention (treatment) to prevent one of the other outcomes.
- required intervention to prevent permanent impairment or damage (for devices only)

Important medical events are those that may not be immediately life threatening but are clearly of major clinical significance. They may jeopardize the subject and may require intervention to prevent one of the other serious outcomes noted above. For example, drug overdose or abuse, a seizure that did not result in in-patient hospitalization, or intensive treatment of bronchospasm in an emergency department would typically be considered serious.

8.3.3 Unanticipated Adverse Device Effect (UADE)

Not applicable.

8.3.4 Classification of an Adverse Event

8.3.4.1 Severity of Event

For adverse events (AEs) not included in the protocol defined grading system, the following guidelines will be used to describe severity.

- Mild – Events require minimal or no treatment and do not interfere with the participant's daily activities.
- Moderate – Events result in a low level of inconvenience or concern with the therapeutic measures. Moderate events may cause some interference with functioning.
- Severe – Events interrupt a participant's usual daily activity and may require systemic drug therapy or other treatment. Severe events are usually potentially life-threatening or incapacitating. Of note, the term "severe" does not necessarily equate to "serious".

8.3.4.2 Relationship to Study Intervention

All adverse events (AEs) must have their relationship to <study intervention> assessed by the clinician who examines and evaluates the participant based on temporal relationship and his/her clinical judgment. The degree of certainty about causality will be graded using the categories below. In a clinical trial, the study product must always be considered.

- Related – The AE is known to occur with the GNB, there is a reasonable possibility that the GNB caused the AE, or there is a temporal relationship between the GNB and event.

Reasonable possibility means that there is evidence to suggest a causal relationship between the GNB and the AE.

- Not Related – There is no temporal relationship between the GNB and event onset, or an alternate etiology has been established.

8.3.4.3 *Expectedness*

The medical director, [name], will be responsible for determining whether an adverse event (AE) is expected or unexpected. An AE will be considered unexpected if the nature, severity, or frequency of the event is not consistent with the risk information previously described for the GNB.

8.3.5 *Time Period and Frequency for Event Assessment and Follow-Up*

Safety will be assessed by monitoring and recording potential adverse effects using the Common Terminology Criteria for Adverse Events (CTCAE) at each study visit. Participants will be monitored by medical histories, physical examinations, and vital signs. If CTCAE grading does not exist for an adverse event, the severity of mild, moderate, severe, life-threatening, and death, corresponding to Grades 1-5, will be used whenever possible.

At each contact with the subject, the investigator will seek information on adverse events by non-directive questioning and, as appropriate, by examination. Adverse events may also be detected when they are volunteered by the subject during the screening process or between visits, or through physical examination, laboratory test, or other assessments. Information on all adverse events will be recorded in the source documentation. To the extent possible, adverse events will be recorded as a diagnosis and symptoms used to make the diagnosis recorded within the diagnosis event.

As much as possible, each adverse event or follow-up information will be evaluated to determine:

1. Severity grade (CTCAE Grade 1-5)
2. Duration (start and end dates)
3. Relationship to the study treatment or process – [Reasonable possibility that AE is related: No (unrelated/ not suspected) or Yes (a suspected adverse reaction)]. If yes (suspected) - is the event possibly, probably or definitely related to the investigational treatment?
4. Expectedness to study treatment or process – [Unexpected – if the event severity and/or frequency is not described in the investigator brochure (if applicable) or protocol].
5. Action taken with respect to study or investigational treatment or process (none, dose adjusted, temporarily interrupted, permanently discontinued, unknown, not applicable)

6. Whether medication or therapy taken (no concomitant medication/non-drug therapy, concomitant medication/non-drug therapy)
7. Whether the event is serious

Once an adverse event is detected, it should be followed until its resolution or until it is judged to be permanent, and assessment should be made at each visit (or more frequently, if necessary) of any changes in severity, the suspected relationship to the study treatment, the interventions required to treat it, and the outcome.

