6 STUDY INTERVENTION

6.1 Study Intervention(s) Administration

6.1.1 *Study Intervention Description*

The study interventions are either conventional analgesia or a one-time three-point GNB with weight-based 0.5% bupivacaine and 4 mL dexamethasone divided into three separate injections, ~~around the SMGN, SLGN, and IMGN. Bupivacaine and dexamethasone are commercially~~ available and are being used in accordance with approved labeling.

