9.4.3 Safety Analyses

Adverse events will be coded as previously described and Section 8. Safety analyses will be reported and presented as summary statistics. For side effects, descriptive statistics and Fisher's exact tests will be performed for possible differences between the treatment arms.

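### The two relatedness rules for adverse events overlap, disagree with each other, and treat the GNB and control arms unequally

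*Protocol*

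**What the plan says.** Protocol 6.1.1 treats both arms as study treatment: "The study interventions are either conventional analgesia or a one-time three-point GNB". Section 8.3.4.2 asks the examining clinician to judge the causal link for each adverse event from its timing and from clinical judgment; the template placeholder for the name of the study intervention was never filled in. The two categories that follow name only the GNB:

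- *Related* has three alternatives joined by *or*. The first is "The AE is known to occur with the GNB". The second and third read "there is a reasonable possibility that the GNB caused the AE, or there is a temporal relationship between the GNB and event".
- *Not Related* has two, also joined by *or*: "There is no temporal relationship between the GNB and event onset, or an alternate etiology has been established".

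Expectedness (8.3.4.3) and the causality question for serious events (8.3.7) are likewise tied to the GNB.

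Section 8.3.5 asks for relatedness a second time. It refers to the study treatment or process, asks whether there is a reasonable possibility of a causal link (No or Yes), and if Yes asks: "is the event possibly, probably or definitely related to the investigational treatment". Timing alone is not a criterion there.

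Section 8.2 describes follow-up "via phone call 24 to 36 hours after the procedure to determine the presence of complications". Section 9.4.3 plans the Fisher method for side effects and says that such "tests will be performed for possible differences between the treatment arms".

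**The concern.** A causality scale should put each event in one category, and a two-arm comparison needs the same question asked in both arms. Section 8.3.4.2 appears to do neither. Its categories can both apply to one event, no rule says which prevails, and it has no usable category for harm caused by a control-arm analgesic. Section 8.3.5 then applies a different test to the same event.

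This matters because the risk/benefit argument in 2.3.3 is that the block spares patients the harms of opioids. A table of treatment-related events built on 8.3.4.2 could not show that benefit. The trial is also open-label (6.3), so the assessor knows the arm when applying a rule that works differently by arm.

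**Working it through.** The plan gives no figure to reproduce, and the point rests on no rate or sample size. The check is a logical enumeration of the wording.

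**Inputs (8.3.4.2).** Four yes/no conditions:
- K: the event type is known to occur with the GNB
- R: there is a reasonable possibility that the GNB caused it
- T: there is a temporal relationship to the GNB
- A: another etiology is established

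**Rules as written.**
- *Related* = K or R or T
- *Not Related* = (not T) or A

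**GNB arm.** Four conditions give 2 × 2 × 2 × 2 = 16 combinations. **Control arm.** No GNB is given, so T and R are both No, and K and A give 2 × 2 = 4 combinations.

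| Situation | Combinations | *Related* only | *Not Related* only | Both |
|---|---|---|---|---|
| GNB arm, T = Yes, A = No | 4 | 4 | 0 | 0 |
| GNB arm, T = Yes, A = Yes | 4 | 0 | 0 | 4 |
| GNB arm, T = No | 8 | 0 | 2 | 6 |
| Control arm | 4 | 0 | 2 | 2 |

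The GNB arm totals 4 *Related* only, 2 *Not Related* only and 4 + 6 = 10 both. These are counts of logical cases, not expected event frequencies, and some are unlikely in practice (for example R = Yes with T = No).

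**Reading the table.**
1. With T = Yes and A = No, the event is *Related* even when K and R are both No, that is, with no causal evidence beyond timing.
2. With T = Yes and A = Yes, both categories apply and nothing in the text decides.
3. Every control-arm event meets *Not Related*. Where K = Yes it meets *Related* as well.

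**Control-arm examples from the protocol's own lists.** Sections 2.1 and 2.3.3 name nausea and respiratory depression as opioid harms. Nausea is also in the bupivacaine profile in 2.2.3. If that profile counts as known with the GNB (an assumption), opioid-induced nausea in a control patient meets both categories. Respiratory depression is not in 2.2.3, so it is *Not Related* only, although a study treatment caused it.

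**8.3.4.2 against 8.3.5.**

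| Event | 8.3.4.2 | 8.3.5 |
|---|---|---|
| GNB arm, soon after the block, type not in 2.2.3, no causal evidence, no other cause established | *Related* (timing alone) | No |
| Control arm, respiratory depression caused by the opioid given | *Not Related* | Yes, if study treatment includes conventional analgesia as in 6.1.1; but the follow-up question concerns the investigational treatment |

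**Where the grade is used.**
- Section 9.4.3 compares side effects by arm and sets no restriction to related events; 9.4.1 says the same.
- Section 8.3.7 requires serious events to be reported whatever their relatedness.
- Section 8.4.1 makes relatedness one of three criteria for an unanticipated problem and defines possible relatedness by reasonable possibility. That is closer to 8.3.5 than to 8.3.4.2, so the recorded 8.3.4.2 grade may not answer the question that 8.4.1 asks.

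**The telephone call.** Section 8.2 ties the check for complications to the procedure. Sections 4.1, 6.4 and 8.1 describe the call in both arms mainly as a check on duration of analgesia. Section 8.3.5 asks about adverse events at each contact, which partly offsets the narrower wording.

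**The case against.** The strongest reply is that little depends on this grade. No adverse-event measure is a primary or secondary endpoint, the planned between-arm test is on side effects, and serious events are reported in any case. A deliberately wide *Related* category for the new procedure can be a cautious safety choice. Section 8.3.5 offers a route to attribute events to control drugs, and its questioning at each contact covers both arms. All of this stands and limits the consequence. It does not remove the overlap between the categories or the conflict between the two sections. Caution toward the GNB also does not explain why harm from a control drug has no clear category.

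A reader might infer more: that almost all GNB-arm events become *Related* and all control-arm events only *Not Related*, so that the Fisher comparison is biased against the block. The documents do not support that, for these reasons:
- In the GNB arm, an established other cause leads to *Not Related*, clinical judgment is part of the assessment, and events between consent and block (8.3.6 starts collection at consent) precede any timing link.
- In the control arm, an event of a type known with the GNB also meets *Related*, and 8.3.5 refers more broadly to study treatment or process.
- No between-arm test of related events is planned, so no distorted p-value follows from the plan.

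**Conclusion.** The point holds as an internal inconsistency of minor severity. Within 8.3.4.2 the categories are not mutually exclusive, timing alone suffices for *Related*, and the reference is to the GNB only although 6.1.1 names two study interventions. Between 8.3.4.2 and 8.3.5 the same event can receive opposite answers.

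The effect is confined to causality records, any by-arm listing of related events, and the relatedness criterion in 8.4.1. Its size cannot be given as a number because the protocol states no adverse-event rates. How many GNB-arm events the timing route would catch depends on what counts as a temporal relationship, which is not defined. With participation ending 24 to 36 hours after treatment, it is reasonable to assume that most events after the block would be close to it in time.

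The conclusion rests on a literal reading of the word *or* in both definitions, and on taking T and R as No when no GNB was given.

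**What to change.** 1. In 8.3.4.2 and 8.3.5, use one scale, graded against the study treatment the participant received (the GNB with its drugs, or the conventional analgesic given), with the same wording in both arms. Fill in the placeholder accordingly.
2. Make the categories complementary. *Related*: a reasonable possibility that the treatment received caused the event, and no other cause established. *Not Related*: no such possibility, or another cause established. Timing and known event types become evidence for the judgment; neither is sufficient alone. If the finer certainty grades in 8.3.5 are kept, nest them under *Related* and name the same treatment.
3. In 9.4.3, confirm that the Fisher comparison uses all adverse events regardless of attribution.
4. In 8.2, reword the existing 24 to 36 hour call so that both arms are asked the same complication questions.

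The cost is protocol wording and one REDCap field, with no added contact, staff or patients. The downside is that more control-arm events will be recorded as related, and GNB-arm events linked by timing alone will no longer be flagged automatically.

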8.3.6 Adverse Event Reporting

Reporting Period

Adverse events will be reported from the time of informed consent until study completion.

Investigator Reporting: Notifying the Study Sponsor

Not Applicable.

Investigator Reporting: Local Reporting Requirements

The investigator will report AEs and SAEs to the IRB/EC of record and other local regulatory groups per the local requirements.

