2.3 Risk/Benefit Assessment

2.3.1 Known Potential Risks

Manufacturer Drug Information:

LAST: As with all local anesthetics, the principal risk of bupivacaine is LAST, as previously described. To mitigate the risk of this, (1) anesthetic will be dosed by ideal body weight to not exceed the limit of safe dosing (e.g., 80% of maximal safe dosing by ideal body weight in patients with BMI greater than or equal to 25 kg/m² and actual body weight in patients with BMI less than 25 kg/m²), (2) anesthetic will be administered slowly to identify any early signs of toxicity, (3) aspiration will be performed prior to each injection to ensure anesthetic will not be administered intravascularly, and (4) real-time ultrasound guidance with color doppler will be performed to visualize blood vessels to ensure anesthetic is not being administered intravascularly. The risk of LAST is extremely low (<1/10,000) ([Neal 2018](#)).

Bleeding: With any percutaneous procedure, there is a risk of superficial and deep tissue bleeding. To minimize this risk, continuous real-time ultrasound visualization of the injection needle will be performed to ensure vasculature is not compromised.

Infection: With any percutaneous procedure, there is a risk of soft tissue infection. To minimize this risk, the skin overlaying the injection sites will be prepped in standard fashion with chlorhexidine, sterile ultrasound probe covers will be used, operators will wear sterile gloves, and single-single use sterile needles will be used for each injection.

Alternative Procedures: Considered using higher concentrations (0.75%), and while these have been proven safe for peripheral use, we elected to proceed with lower concentration (0.5%) for safety. Preliminary (non-published) data suggests that weight-based dosing of 0.5% bupivacaine can produce desired anesthesia. We will use ultrasound-guidance rather than landmark-guidance to visualize and avoid the genicular arteries that lay in proximity to the genicular nerves ([Callese 2023](#)).

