The control arm will be treated with oral, intravenous, or topical analgesics, as per the treating clinician's discretion. Patients will be observed on continuous cardiorespiratory monitoring in the ED for at least 30-minutes following treatment to evaluate for treatment effect and adverse events. Patients will be discharged from the ED when their pain is sufficiently controlled, and they are agreeable for discharge. Of note, patients in both treatment arms will be eligible for additional analgesics, as needed, at any point after enrollment. This will be recorded and evaluated during analysis. At either 1-hour after enrollment or at the time of discharge from the ED (whichever occurs first), patients of both treatment arms will be again asked to rate their pain severity on the NRS and asked to complete the modified APS-POQ-RED. This survey will be conducted either by RAs (during daytime hours, if available) or the performing physician (if overnight). Patients will subsequently receive a phone call approximately 24 to 36 hours after the treatment by a member of the study team (performing physician, RA, or the clinical research coordinator (CRC) from the Emergency Ultrasound Division) to evaluate the duration of analgesia. If the block is performed during overnight hours, the follow-up call will take place the next day (between 24 to 36 hours after treatment). After this assessment, the participant's involvement in the study will be concluded. Only in cases where an adverse event occurred that either requires hospitalization or ambulatory follow-up will a participant's participation last longer than 24 hours. All data collected by the RA, the CRC, or the performing physician will be stored in REDCap. The RAs will transmit all research data, including an encrypted medical record number (MRN) and all pain scale responses obtained from the study participants to the Ultrasound Division's CRC, who will be responsible for storing and managing data on REDCap.

Patients with large knee effusions will not be included in the study as large effusions can make the GNB more difficult to perform by distorting the anatomical and sonographic landmarks, and we wish to avoid the additional risk of inadvertent intra-articular injections. In our experience, we have been able to perform the GNB on patients with small and moderate sized effusions without difficulty.

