4.4 End of Study Definition

A participant will have completed this study at 24 to 36 hours after blockade, when the research assistant or performing physician will contact the patient via telephone for follow-up assessment, to evaluate for duration of analgesia. For patients that experience an adverse event that requires admission to the hospital or ambulatory follow-up, their participation in the study might be extended beyond 24 to 36-hours as these adverse events and outcomes will be tracked.

Patients who receive the GNB and rate their pain on the NRS before and after the procedure, even those who refuse the APS-POQ-RED survey responses and who are not available to be reached by phone the next day, will still be included in the data analysis for the primary and one secondary endpoint (pain levels, LOS).

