7.3 Lost To Follow-Up

A participant will be considered lost to follow-up if he or she does not respond via telephone at the 24-hour follow-up after three attempts by the participating emergency physician or clinical research assistant. However, patient intervention and any outcome data that has previously been obtained (e.g., data collected at time of discharge from the ED) will still be included. All participants who complete the initial assessment by the time of discharge will be included in the analysis. No follow-up visits will be required.

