8.3.8 Reporting Events to Participants

Any expected adverse events are anticipated to occur within the first 30 minutes of the GNB, such that all participants will be monitored during that time in person. Any concerns of potential adverse events will be communicated to participants at this time.

8.3.9 *Events of Special Interest*

Not applicable.

8.3.10 *Reporting of Pregnancy*

Not applicable.

8.4 *Unanticipated Problems*

8.4.1 *Definition of Unanticipated Problems (UP)*

The Office for Human Research Protections (OHRP) considers unanticipated problems involving risks to participants or others to include, in general, any incident, experience, or outcome that meets all the following criteria:

- Unexpected in terms of nature, severity, or frequency given (a) the research procedures that are described in the protocol-related documents, such as the Institutional Review Board (IRB)-approved research protocol and informed consent document; and (b) the characteristics of the participant population being studied;
- Related or possibly related to participation in the research (“possibly related” means there is a reasonable possibility that the incident, experience, or outcome may have been caused by the procedures involved in the research); and
- Suggests that the research places participants or others at a greater risk of harm (including physical, psychological, economic, or social harm) than was previously known or recognized.

8.4.2 *Unanticipated Problem Reporting*

Unanticipated problems (UPs) such as:

- Post-marketing withdrawal of a drug, device, or biologic used in a research protocol due to safety concerns.
- FDA ban of a drug, device, or biologic used in a research protocol due to safety concerns.
- Complaint of a participant when the complaint indicates unexpected risks, or the complaint cannot be resolved by the research team
- Breach of confidentiality
- Incarceration of a participant when the research was not previously approved under Subpart C and the investigator believes it is in the best interest of the subject to remain on the study
- Premature closure of a study (e.g., due safety, lack of efficacy, feasibility, financial reasons, etc.)

should be reported by the investigator to the medical director. The UP report will include the following information:

- Protocol identifying information: protocol title and number, PI's name, and the IRB project number;
- A detailed description of the event, incident, experience, or outcome;

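### Active adverse event collection stops at the 24-36 h call, so an infection that first appears later has no planned route into the safety data, and a zero count is not evidence of no risk

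*Protocol*

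**What the plan says.** Section 2.3.1 of the protocol lists three known risks of the block: local anesthetic systemic toxicity (LAST), bleeding and infection. On the last it says "With any percutaneous procedure, there is a risk of soft tissue infection".

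The collection period is set in several places:

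- Section 8.3.6: "Adverse events will be reported from the time of informed consent until study completion". Study completion is not defined there.
- Section 4.4: "A participant will have completed this study at 24 to 36 hours after blockade".
- Section 4.1, on the follow-up call: "After this assessment, the participant's involvement in the study will be concluded".
- Section 8.2: the treating physician or the research coordinator "will follow up with patients via phone call 24 to 36 hours after the procedure to determine the presence of complications".
- Section 7.3: "No follow-up visits will be required".

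There is one extension, in section 4.1: "Only in cases where an adverse event occurred that either requires hospitalization or ambulatory follow-up will a participant's participation last longer than 24 hours". Section 4.4 has a similar provision, and section 8.3.5 asks that an event, once detected, be followed to resolution.

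Section 8.3.8 says "Any expected adverse events are anticipated to occur within the first 30 minutes of the GNB". Section 9.4.3 plans summary statistics for safety and Fisher's exact tests of side effects between the arms.

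**The concern.** Only the block arm receives the three study punctures, so injection-site infection is a harm that the trial itself can cause in one arm. The schedule of safety contacts (30 minutes of observation, then one call) suits an early event such as LAST. It is not shown to suit infection, and section 8.3.8 speaks of expected events as if infection were not among them.

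What is at stake is how a zero would be read. Section 2.3.3 already describes an excellent safety profile, based on anatomy, the absence of published complications and the team's own experience. A trial report of no infections would seem to confirm that, although the plan has no means of finding an infection that starts after the call. A statistical analysis plan cannot repair this, because the data would not have been collected.

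**Working it through.** **Does any provision catch a late event?**

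1. The call is the last scheduled contact (sections 4.1, 8.2), and no later visit is required (section 7.3).
2. The extensions in sections 4.1, 4.4 and 8.3.5 apply to an event that has already occurred or been detected. They lengthen follow-up of a known event and do not look for a new one.
3. If study completion in section 8.3.6 means the end of the 12-month study, a late spontaneous report could count. No contact or record check is scheduled to obtain one.
4. A participant not reached after three attempts (section 7.3) has no planned safety information after discharge. Section 9.2 expects 5-10% loss at this point: 0.05 × 34 = 1.7 to 0.10 × 34 = 3.4, so about 2 to 3 participants.

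**How much could be missed?** The protocol gives no safety figure to reproduce. Inputs: n = 17 in the block arm (section 9.2); p, the true infection rate, and f, the share of infections showing by 36 h. Both p and f are assumptions.

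Chance of recording at least one infection = 1 − (1 − p·f)^17:

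| f | p = 1% | p = 5% |
|---|---|---|
| 0 | 0% | 0% |
| 0.10 | 1.7% | 8.2% |
| 0.25 | 4.2% | 19.3% |
| 0.50 | 8.2% | 35.0% |
| 1.00 | 15.7% | 58.2% |

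Example: p = 5%, f = 0.25 gives 1 − (1 − 0.0125)^17 = 0.193.

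**What does 0 of 17 exclude?** With full detection, the one-sided 95% upper limit is 1 − 0.05^(1/17) = 0.162. With a share f detected, the limit on the true rate is 0.162/f:

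- f = 0.5: 32%
- f = 0.25: 65%
- f = 0.1: above 100%, so no bound

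Loss at the call alone matters little. With 16 reached the limit is 1 − 0.05^(1/16) = 0.171, and with 15 reached it is 1 − 0.05^(1/15) = 0.181.

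**What would the between-arm test show?** With no control infections, Fisher's two-sided test gives p = 0.103 for 4 of 17 against 0 of 17 and p = 0.044 for 5 against 0, so five infections are needed. Even with full detection its power is about 0.1% at a 5% rate and 2.2% at a 10% rate.

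**The case against.** A reader might infer that the safety comparison will show no infections whatever the truth. The documents do not support that. It would require f = 0, and the protocol gives no time to onset. The call in section 8.2 is made to look for complications, so an early infection can be recorded, and one needing admission or ambulatory follow-up would be tracked. How many infections appear after 36 hours cannot be established from the protocol, which is why the table runs over the whole range of f.

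A reader might also infer that nothing later could ever be found. That too goes too far. Section 8.3.5 accepts events that a participant volunteers between visits, and section 8.3.7 requires serious events to be reported immediately. The alert for emergency patients with knee pain (section 4.1) is a recruitment tool, but it might flag a participant who returns. These routes are passive and depend on chance, but they exist.

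The strongest objection is that the small sample explains a zero as well as the window does. With complete detection and a 1% rate, the chance of seeing any infection is only 15.7%, and no realistic extension makes Fisher's test informative. This stands: the window is not the sole cause. It does not remove the point, since in a trial this small one missed case is the difference between none and 1 of 17 (5.9%).

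Finally, safety is not among the objectives or endpoints in section 3, and the statement in section 2.3.3 is background rather than a hypothesis. That lowers the weight of the point. Even so, section 9.4.3 plans to compare side effects between the arms, so what can enter that comparison should be fixed properly. Keeping participants lost to the call in the analysis dataset (section 9.3) is correct and is not criticised here.

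**Conclusion.** The point holds in a limited form. Active collection of adverse events ends for each participant at the 24-36 h call, and an infection first appearing after it, or in a participant not reached, has no planned route into the safety data. A zero count cannot be read as absence of infection risk.

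The size depends on f, which the protocol does not give. At an assumed 5% rate, the chance of recording any infection falls from 58.2% with full detection to 19.3% at f = 0.25 and 8.2% at f = 0.1. Even with full detection, 0 of 17 excludes only rates above about 16%.

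Two textual faults are independent of any assumption: study completion is undefined in section 8.3.6, and section 8.3.8 does not fit the inclusion of infection in section 2.3.1. The point does not affect the efficacy analysis. It is worth acting on because the remedy is cheap and recovers data that would otherwise not be sought.

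**What to change.** - **Sections 8.3.6 and 4.4:** define study completion for adverse event reporting, and say whether it is the participant's last assessment or the end of the trial.
- **Sections 8.2, 8.3.6 and 4.4:** add one review of the health-system electronic record per participant, in both arms, at a fixed later date. Fourteen days is an example, and the investigators should justify their choice. The review should look for infection, return to the emergency department and admission, and should include participants not reached by phone.
- **Sections 8.3.8 and 2.3.1:** reconcile the stated timing of expected events with infection as a named risk.
- **Section 9.4.3:** state that delayed harms are incompletely assessed and that a zero count is not evidence of no risk. If the review is not added, this sentence is the minimum.

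The cost is about 34 chart reviews, in a record system already used for length of stay (section 9.4.2), and a sentence in the consent form. Care outside the health system would still be missed, and the between-arm test would remain uninformative at 17 per arm. The gain is more complete ascertainment, not a powered safety comparison.
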